10.1 Blinding

Trial participants, the investigator and all other personnel directly involved in the conduct of the trial will be blinded to the individual treatment assignments.

For the MA1 the IDMC and Sponsor will be unblinded, the blind will, however, be kept for patients and investigators until FA1.

To maintain the blind, IMU-838 and placebo tablets will have identical appearance, shape and color, and will have identical labeling and packaging. To minimize the potential for bias, treatment randomization information will be kept confidential by the responsible personnel and will not be released to investigators, other trial center personnel, or the Sponsor's designee(s).

10.2 Emergency unblinding

The premature breaking of the blind will be restricted to emergency cases in which knowledge of the administered drug is necessary for treatment of clinically significant AEs. Whenever possible but not required in emergency situations, the investigator must contact the Sponsor or the medical monitor before breaking the blind and evaluate if the knowledge of the administered drug would have any impact on treatment decisions for the AE. If the blind is broken, the respective patient will be withdrawn from further treatment in this trial and a written explanation must be given by the investigator to the Sponsor immediately. Emergency unblinding, if necessary, will be conducted via the interactive web-based response system (IWRS) of the electronic case report from (eCRF).

10.3 Patient identification

A 7-digit patient identifier consisting of 2 digits each for country (YY), center (XX) and 3 digits for patient (ZZZ) i.e., YYXX-ZZZ will be assigned to each screened patient.

10.4 Randomization

Patients will be randomly assigned to treatment groups by means of a computer-generated randomization list with a 1:1 allocation. Randomization will be done by an IWRS within the eCRF.

Patients will be assigned respective IMP kits. The investigators will be provided with technical options and password information to selectively break the code for an individual patient in case of emergency via the IWRS (back-up by phone maybe established).

11 Treatments

11.1 Investigational medicinal product

All IMPs supplied by the Sponsor will be manufactured, tested, and released according to current Good Manufacturing Practice guidelines and local requirements.

11.1.1 IMU-838

Name:	IMU-838
Manufacturer:	Immunic AG
Active ingredient:	Vidofludimus calcium (IM90838)
Inactive ingredients:	Microcrystalline cellulose EP, polyvidon K25, crospovidone EP type A, talc, and magnesium stearate
Formulation:	Tablets containing a specific polymorph of vidofludimus calcium
Matrix:	White uncoated tablets, biconvex shape, diameter of 8 mm
Dose strength:	22.5 mg
Total daily dose:	45 mg

11.1.2 Placebo

The placebo tablets will be identical to the IMU-838 tablets in terms of appearance, constitution of inactive ingredients, and packaging.

11.1.3 Packaging, labeling and dispensing

All IMP will be packed and labeled according to applicable regulatory requirements.

The labels will contain at least the following information: route of administration, trial code, randomization number, batch number, expiry date, and instructions for storage.

IMU-838 and placebo tablets will be packaged in 30 mL polyethylene bottles containing 32 tablets.

For patients discharged from the hospital before Day 14, the patient will be allowed to take the IMP home to complete blinded treatment (*not applicable for centers in Bulgaria as all patients must be hospitalized between Day 0 and Day 14*).

11.1.4 Storage and stability

The investigator is responsible for the safe and proper handling and storage of the IMP at the investigational site. The IMP must be stored in a locked facility with access limited to the investigator and authorized personnel. The investigator must ensure that the IMP is administered only to patients enrolled in this trial.

In stability studies, IMP was stable at ambient (25°C/60% relative humidity) and at accelerated storage conditions (40°C/75% relative humidity) and does not require any special storage conditions. However, the tablets should be protected from direct sun light, moisture, freezing, and extended periods of excessive heat (defined as any temperature above 40°C [104 F]). It should also be advised to keep the bottle tightly closed to protect tablets from moisture.

11.1.5 Treatment dose, dose selection, and administration

Tablets will be taken BID with a glass of water (if possible); one tablet each in the morning (15 to 50 min before a meal if applicable), and in the evening (2 hours after any meal if applicable).

The 1st IMP dose on Day 0 should always be the “evening dose of Day 0”. To administer the 1st IMP dose as close as possible to time of randomization, the initial IMP dose (“evening dose of Day 0”, 2 tablets to be given at once) can be administered between 12:00 noon on Day 0 to 02:00 a.m. on Day 1. The 2nd IMP dose is then given in the morning of Day 1, and dosing continues twice daily until the evening dose of Day 13 (last IMP dose). Except for the initial IMP dose (2 tablets), all other IMP doses will consist of 1 tablet. The timing of morning and evening doses (except for initial evening dose on Day 0) should be at the same time of the day, if possible (see [Table 2](#)).

Table 2: Administration of tablets

Time	Day 0		Day 1		Days 2 to 12		Day 13	
	AM	PM	AM	PM	AM	PM	AM	PM
Number of tablets		2	1	1	1	1	1	1
Dose IMU-838		45 mg	22.5 mg	22.5 mg	22.5 mg	22.5 mg	22.5 mg	22.5 mg
		#	*	*	*	*	*	*

Day 0: Loading dose of 45 mg IMU-838 once daily given in the evening of Day 0.

* Day 1- Day 13: dosing of 22.5 mg IMU-838 BID (twice daily).

If the patient is intubated for ventilation, IMP is to be given via a gastric tube. The tablet has no coating and a homogeneous content and can be crushed into smaller pieces (if necessary) for dosing via gastric tube.

If the patient is discharged from the hospital before Day 14, the patient will receive the IMP and will take the remaining doses of IMP at home (*not applicable for centers in Bulgaria as all patients must be hospitalized between Day 0 and Day 14*).

The 45 mg dose used in this trial is on the higher end of doses used in completed and ongoing clinical trials. A daily dose of 50 mg IMU-838 was found to be safe in a 14-day Phase 1 clinical trial (Trial P1-IMU-838-MAD). The 45 mg dose is also used in the ongoing Phase 2 studies in multiple sclerosis (P2-IMU-838-MS) and ulcerative colitis (P2-IMU-838-UC). In an interim analysis of Trial P2-IMU-838-UC during which unblinded safety data were evaluated by an independent Data Review Committee, no safety signal was found, and the 45 mg dose was considered as not intolerable. Based on the overall safety data, 45 mg IMU-838 is considered a safe dose. To maintain IMU-838 drug levels as stable as possible, the dose of 45 mg IMU-838 is to be given as 22.5 mg dose BID in this trial.

For patients with a hyperacute disease like COVID-19, it is imperative that therapeutic drug levels are quickly reached. Because of the short half-life (approximately 30 hours) and short time to maximum blood levels (3-4 hours after oral dosing) of IMU-838, therapeutic levels are reached rather quickly. In addition, the first dose (loading dose in the evening of Day 0) will be given as 45 mg dose of IMU-838 (2 tablets of 22.5 mg IMU-838 taken at the same time). This will ensure that therapeutic drug levels are expeditiously reached in this hyperacute disease.

The PK profile of IMU-838 based on the described dosing (loading dose of 45 mg IMU-838 on Day 0, then 22.5 mg IMU-838 BID for the remaining treatment days) should therefore result in a profile with a quick onset of therapeutic effects and stable therapeutic drug level over the 14-day treatment period.

11.1.6 Drug accountability and patient compliance

The IMP must not be used outside the context of this trial protocol. For patients discharged from the hospital the investigator must ask the patient to return excess IMP and all packaging materials (including empty containers) at Day 14 (see [Table 3](#)) for drug accountability. Unused IMP cannot be used outside the context of this trial protocol. Dispensed and returned IMP cannot be re-used for any other patients.

The investigator or authorized staff must document the receipt, dispensing, and return of all IMP received during this trial. These records will include but are not limited to dates, quantities, batch numbers, patient identifiers, and unique interactive response technology codes, as applicable. The investigators must maintain records documenting that patients were provided with the IMP as outlined in the protocol. Furthermore, investigators will reconcile all IMP received from the Sponsor and administered to or returned from the patient. It is the responsibility of the investigator to reason any discrepancies in IMP accountability. Forms will be provided to ease accountability.

At the end of the clinical trial, or as directed, all remaining and unused IMP must be accurately counted (final drug accountability) and destroyed according to the Sponsor's instructions, i.e., to e.g., return all remaining and unused IMP to the Sponsor or Sponsor's designee.

11.2 Prior and concomitant medications

All medications administered within 2 days before the day of informed consent and until EoS must be documented in the corresponding section of the eCRF. Vasopressor dose will be documented separately.

All medications taken by the patients after giving informed consent and all treatments given in addition to the IMP during the trial are regarded as concomitant treatments and must be documented in the eCRF.

11.2.1 Standard of care treatment and concomitant treatments

Any treatments, medications and procedures that investigators would customarily use to treat COVID-19 in their clinical practice should be included in SoC treatment. The investigator's choice of SoC can include supportive pharmaceutical treatments (including medications that are approved in other indications but that the investigator customarily uses in COVID-19 patients), medications with any approved antiviral indication, intravenous fluids, supplemental oxygen, noninvasive and invasive ventilation, antibiotic agents, vasopressor support, RRT, and ECMO. Investigational treatments not yet approved for commercial use in the respective country (for example obtained through an early access program) or parallel participation in different interventional trials are prohibited in this trial.

In addition, Arbidol and Colchicine are prohibited for centers in all countries. Chloroquine and Hydroxychloroquine are also prohibited for all centers in all countries unless already taken for indicated use before entering the trial.

11.2.2 Prohibited and restricted medication

The use of the following medications and treatments will be prohibited from Screening to end-of-treatment with IMP in this trial (up to Day 14) if not indicated otherwise in this protocol:

- Concurrent use of any mycophenolate mofetil or of methotrexate exceeding 17.5 mg weekly
- Any medication known to significantly increase urinary elimination of uric acid, in particular lesinurad (ZurampicTM) as well as uricosuric drugs such as probenecid
- Current treatments for any malignancy, in particular irinotecan, paclitaxel, tretinoin, bosutinib, sorafenib, enasidenib, erlotinib, regorafenib, pazopanib and nilotinib
- Any drug significantly restricting water diuresis, in particular vasopressin and vasopressin analogs
- Use of rosuvastatin at daily doses higher than 10 mg
- Arbidol and Colchicine
- Any use of other DHODH inhibitors, including teriflunomide (AubagioTM) or leflunomide (AravaTM)
- Chloroquine and Hydroxychloroquine are not allowed during the entire trial, unless already taken for indicated use before entering the trial

Routine use of steroids is not recommended and should be reserved for patients with severe disease or with special circumstances. Concomitantly used steroids (e.g., required for pre-existing conditions) do not need to be discontinued when entering this trial, however, their use should be carefully considered.

After the 14-day treatment period with IMP any drugs to treat the disease, including any anti-viral therapy, can be used at the investigator's discretion.

The concomitant administration of drugs metabolized for more than 70% by CYP2C8 (although not prohibited) should be carefully considered since it cannot be excluded that IMU-838 potentially increases their blood levels. Major substrates of CYP2C8 include:

- amodiaquine (anti-malarial)
- dasabuvir (anti-viral),
- enzalutamide (anti-cancer)
- montelukast (anti-asthmatic), and
- pioglitazone and repaglinide (anti-diabetics)

The use of the potent CYP2C8 inhibitor rifampicin and strong and moderate CYP2C8 inducers gemfibrozil and trimethoprim as concomitant medication is not prohibited during this trial. However, alternatives to these drugs should be considered, and patients should be carefully monitored for any indication of toxicity. Given the known narrow therapeutic window of ibuprofen, the use of ibuprofen should be carefully considered or, if possible, therapeutic alternatives should be used.

12 Trial schedule

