The first dose of IMP (2 tablets) should always be given on Day 0 (allowed range for first dose: 12:00 noon on Day 0 to 02:00 a.m.). All further IMP doses are 1 tablet each in the morning and evening. For details of IMP administration see section [Test product](#). Information about the status and patient care are continuously obtained and documented once or twice daily (see [Table 1](#)). Further examinations and tests, laboratory parameters, biomarkers, disease markers, and virologic parameters are to be assessed as outlined in [Table 1](#).

After the last IMP dose in the evening of Day 13, the end-of-treatment (EoT) assessments will be done on Day 14 (see [Table 1](#)). Blood sampling for IMU-838 trough values must be performed in the morning around the time the morning dose was usually taken by the respective patient. Patients may then continue to receive SoC without any further restrictions on concomitant medications as during the 14-day BT period (see [Standard-of-care treatment](#) and [IMP-related exclusion criteria](#)).

For centers in Bulgaria: Patients must be hospitalized during the entire treatment period i.e., from Day 0 to Day 14.

For centers in countries other than Bulgaria: In case of hospital discharge before Day 14, the following assessments should be done between hospital discharge and until Day 14 (patients should return for clinic visits at Day 6, if discharged before Day 6, and Day 14):

- On the day of hospital discharge:
 - All trial-related assessments and procedures are completed as per [Table 1](#) and finalized (evening assessments should be done, even when the patient is discharged during the day)
 - The date and time of hospital discharge need to be documented
- Day 6 and Day 14:
 - The full lab assessments to be performed on Days 6 or 14, respectively (as indicated in [Table 1](#))
 - Physical examination and ECG
 - Documentation of concomitant medications/procedures, AEs, temperature, vital signs, respiratory rate, type of oxygen supplementation, survival status, hospitalization status, assessment of WHO ordinal scale¹ (only once daily assessment required)
 - Return of IMP by patients and drug accountability (Day 14 only)

If the patient is discharged from the hospital before Day 14, the patient will receive the IMP and will take the remaining doses of IMP at home.

Day 28 Visit (EoS)

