The first dose of IMP (2 tablets) should always be given on Day 0 (allowed range for first dose: 12:00 noon on Day 0 to 02:00 a.m.). All further IMP doses are 1 tablet each in the morning and evening. For details of IMP administration see Section 11.1.5. Information about the status and patient care are continuously obtained and documented once or twice daily (see [Table 3](#)). Further examinations and tests, laboratory parameters, biomarkers, disease markers, and virologic parameters are to be assessed as outlined in [Table 3](#).

After the last IMP dose in the evening of Day 13, the end-of-treatment assessments will be done on Day 14 (see [Table 3](#)). Blood sampling for IMU-838 trough values must be performed in the morning around the time the morning dose was usually taken by the respective patient. Patients may then continue to receive SoC without any further restrictions on concomitant medications as during the 14-day BT period (see Section 11.2.1 and [IMP-related exclusion criteria](#)).

The assessments to be performed in case of hospital discharge before Day 14 are described in Section 12.3. *For centers in Bulgaria only: Patients must be hospitalized during the entire treatment period i.e., from Day 0 to Day 14.*

Day 28 Visit (EoS)

The patient should return for the final trial visit on Day 28 (EoS). If IMP is prematurely discontinued for any reason, the EoS visit should always be conducted on Day 28 and no earlier EoS should be performed. If patients withdraw from IMP prematurely, they should be encouraged to allow the EoS visit as part of the follow-up. If the patient dies during the trial, the investigator should indicate that this visit was not performed. However, even if no EoS visit was performed, information about patient status should be reported on the EoS page in the case report form. If the patient refuses any EoS visit or the patient is lost to follow-up, it is permissive in this trial that the investigator contacts the patient, the family of the patient or the referring physician by phone or email to obtain status of life information, or is able to search in registers or publicly available information for such status of life information.

Safety follow up

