 - Current treatments for any malignancy, in particular irinotecan, paclitaxel, tretinoin, bosutinib, sorafenib, enasidenib, erlotinib, regorafenib, pazopanib and nilotinib
 - Any drug significantly restricting water diuresis, in particular vasopressin and vasopressin analogs
 - Use of rosuvastatin at daily doses higher than 10 mg
 - Arbidol and Colchicine
 - Any use of other DHODH inhibitors, including teriflunomide (AubagioTM) or leflunomide (AravaTM)
 - Chloroquine and Hydroxychloroquine during the entire trial unless taken for indicated use before entering the trial
12. Patients with clinically relevant conditions leading to hyperuricemia
13. Use of any investigational product within 8 weeks or 5x the respective half-life before the date of informed consent, whichever is longer, and throughout the duration of the trial

General exclusion criteria

14. Patients who have a “do not intubate” or “do not resuscitate” order (unless the patient waives in writing this order and will allow intubation for the duration of the trial period)
15. Patients with pre-existing end-stage liver disease (Child Pugh B and C score)
16. Patients with known Gilbert syndrome (unless their indirect [unconjugated] bilirubin level is confirmed to be <1.2 x ULN, i.e. <1.1 mg/dL)
17. Patients with known acute or clinically relevant chronic renal failure, patients currently on dialysis, as well as patients with an estimated glomerular filtration rate value <30 mL/min/1.73 m² body surface area according to the Chronic Kidney Disease Epidemiology Collaboration (CKD-EPI) equation for adults (or the Schwartz bedside equation for children and adolescents, if applicable)
18. History or presence of serious or acute heart disease such as uncontrolled cardiac dysrhythmia or arrhythmia, uncontrolled angina pectoris, cardiomyopathy, or uncontrolled congestive heart failure (New York Heart Association [NYHA] class 3 or 4)

Note: NYHA class 3: Cardiac disease resulting in marked limitation of physical activity. Patients are comfortable at rest. Less than ordinary activity causes fatigue, palpitation, dyspnea, or anginal pain. NYHA class 4: Cardiac disease resulting in inability to carry on any physical activity without discomfort. Symptoms of heart failure or the anginal syndrome may be present even at rest. If any physical activity is undertaken, discomfort is increased.

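### For Days 15–28 the protocol both bans and allows newly started chloroquine/hydroxychloroquine; enforcing the ban after a start can replace observed key secondary outcomes with imputed failures (minor)

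*Combined protocol and SAP*

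**What the plan says.** **The ban.** The list in 11.2.2 opens with a default window: the listed drugs "will be prohibited from Screening to end-of-treatment with IMP in this trial (up to Day 14) if not indicated otherwise in this protocol". The chloroquine/hydroxychloroquine (CQ/HCQ) item departs from that default: "Chloroquine and Hydroxychloroquine are not allowed during the entire trial, unless already taken for indicated use before entering the trial". Exclusion criterion 11 in 9.3 agrees: "Chloroquine and Hydroxychloroquine during the entire trial unless taken for indicated use before entering the trial". Section 11.2.1 gives no end date: "Chloroquine and Hydroxychloroquine are also prohibited for all centers in all countries unless already taken for indicated use before entering the trial".

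**The permission.** Later in 11.2.2: "After the 14-day treatment period with IMP any drugs to treat the disease, including any anti-viral therapy, can be used" at the investigator's discretion. The synopsis and 8.1 both say, of the time after the Day 14 assessments: "Patients may then continue to receive SoC without any further restrictions on concomitant medications as during the 14-day BT period". In 8.1 that sentence points to 11.2.1 and to the IMP-related exclusion criteria, which are places where the ban is written.

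**The consequence of a breach.** Section 17.2 lists use of a prohibited concomitant medication, by reference to 11.2, among the reasons for mandatory withdrawal from the trial (not only from study drug). It sets no time limit. Section 12.3 puts the last dose on the evening of Day 13.

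**Handling of discontinued patients in 16.3.2.** For respiratory failure and for ICU duration, two groups are imputed: patients lost or discontinuing by Day 13 for reasons other than death, and patients who discontinue with a last WHO score not below the Screening score. The second group carries no day limit. These patients count as respiratory failures. Their ICU time runs to Day 28 from the discontinuation date, or from the actual admission if an ICU stay is known. For the primary endpoint the two conditions are joined, so the Day 13 limit covers both.

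**Data still sought.** Section 12.5 asks for the Day 28 assessments after premature discontinuation where possible, and 11.2 requires medications to be recorded until end of study.

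**The concern.** Two sites could handle identical patients differently between Day 15 and Day 28, and each could point to current protocol text. The protocol also stratifies on CQ/HCQ as a category of antiviral therapy, so the permission for any antiviral cannot easily be read as leaving these drugs out.

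The statistical interest lies in what follows a start. Withdrawal at this stage stops no study drug, because none is being given; it only changes how the patient is analysed. The patients likeliest to receive an added drug after Day 14 are those who are not improving (an assumption, but a natural one), and non-improvement is also the condition that triggers the imputation. The replacement of data would therefore be linked to outcome. It would fall on two key secondary endpoints that feed the activity decision at MA1, for patients whose real Day 28 outcome could be known.

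**Working it through.** The plan states no figure on this point, so there is none to reproduce. The check is a reading of the text followed by simple arithmetic.

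**Step 1: which rule applies on Days 15–28?**

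| Place | New CQ/HCQ, Days 15–28 |
|---|---|
| 9.3, criterion 11 | banned (entire trial) |
| 11.2.2, list item | banned (entire trial) |
| 11.2.1 | banned, no end date |
| 11.2.2, later sentence | allowed, no exception |
| 8.1 and synopsis | restrictions lifted after Day 14 |

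No sentence gives either rule precedence. Use for an indication that predates the trial is exempt throughout.

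**Step 2: when does withdrawal arise?**

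- A site that reads the ban as binding does not start the drug: no withdrawal.
- A site that reads the permission as binding starts it and sees no breach: no withdrawal.
- The drug is started under the permissive reading, or by a prescriber outside the trial, and the ban is then enforced (for example by the site, a monitor or the sponsor): 17.2 requires withdrawal.

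Only the third path does harm.

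**Step 3: who is then imputed?** Patients whose last WHO score is not below the Screening score. Table 3 schedules daily scores to Day 13, then Day 14 and Day 28. The last score is therefore normally Day 14, unless an unscheduled or Day 28 score counts as the last one. Improved patients are not imputed.

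**Step 4: size per patient.** Imputed ICU days = 28 − withdrawal day if there was no ICU stay, or 28 − admission day if there was one (whole days; the one-minute term in the 16.3.2 formula is ignored).

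| Patient | Observed (example) | Imputed |
|---|---|---|
| No ICU, withdrawn Day 15 | 0 | 28 − 15 = 13 |
| No ICU, withdrawn Day 16 | 0 | 28 − 16 = 12 |
| No ICU, withdrawn Day 21 | 0 | 28 − 21 = 7 |
| No ICU, withdrawn Day 27 | 0 | 28 − 27 = 1 |
| ICU Day 8 to Day 10, withdrawn later | 10 − 8 = 2 | 28 − 8 = 20 |

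Each of the four patients without an ICU stay, if otherwise free of respiratory failure, also becomes a failure. The patient with the ICU stay is a failure already, because need of ICU is part of the definition.

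**Step 5: size per arm.** Take 100 per arm (about 200 patients at MA1) and the same number p per 100 surviving without respiratory failure in both arms. The documents do not give p. The planning rates for need of invasive ventilation are 32% and 40%, and that need counts as respiratory failure, so p would be at most 100 − 32 = 68 and 100 − 40 = 60 under those rates. I show 50 to 90.

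- One net patient reclassified in one arm changes the relative difference by p/(p − 1) − 1. For p = 50: 50/49 − 1 = 2.0%. For p = 60: 60/59 − 1 = 1.7%. For p = 90: 90/89 − 1 = 1.1%. The sign depends on the arm.
- The smallest net k with p/(p − k) ≥ 1.10 is 5 for p = 50 (50/45 = 1.11), 6 for p = 60 (60/54 = 1.11), 7 for p = 70 (70/63 = 1.11), 8 for p = 80 (80/72 = 1.11) and 9 for p = 90 (90/81 = 1.11).
- Equal numbers in both arms leave a null difference at zero.
- One 12-day imputation moves an arm's mean ICU duration by 12/100 = 0.12 days. The MA1 criterion compares medians (about 1.5 days), and the median stays at 0 if fewer than half the arm has any ICU time (assumption).

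**The case against.** **The specific rule prevails.** The list in 11.2.2 allows exceptions to its Day 14 limit, and the CQ/HCQ item is one. The sentence in 8.1 and the synopsis may release only restrictions tied to the treatment period. That is a fair reading of 8.1 and the synopsis. It does not remove the conflict inside 11.2.2, where the later sentence covers any drug and names antivirals.

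**The harm needs two readings in sequence.** This stands. It requires a start under one rule and enforcement under the other, or an outside prescription, which keeps the numbers down.

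**The missing Day 13 limit may be loose drafting.** The primary-endpoint rule joins the two conditions. If that was the intent throughout, Day 15–28 withdrawals are not imputed at all. This is possible, but the wording for respiratory failure and ICU duration differs, and an analyst programs what is written.

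**The schedule limits the exposure.** A Day 28 score may count as the last one, which would spare patients improved by then. For discharged patients, medication use is next due for recording at Day 28, when follow-up is complete. Both points stand.

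**Safeguards exist.** Part 1 has no formal tests, deviations are classified at a blind review, and available-data sensitivity analyses are planned. These reduce the harm but leave the main analysis as it is. The ICU sensitivity analysis uses data only up to the day of discontinuation, so it would not use ICU data collected afterwards.

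**Stronger readings that the text does not support.** A reader might infer that these patients fail the primary endpoint. Under 16.3.2 they do not; only the synopsis wording, which lacks the Day 13 limit on the second group, could reach it. A reader might also infer imputed deaths. The mortality rule counts discontinued patients as deaths only if survival status cannot be obtained, and here the site is normally in contact with the patient.

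**Conclusion.** The contradiction is real and stands in current text. Its consequence is conditional: a patient must start CQ/HCQ after Day 14, the ban must then be enforced, and the last WHO score must be no better than at Screening. On the literal wording of 16.3.2, that patient becomes a respiratory failure with 1 to 13 imputed ICU days (withdrawal on Day 27 to Day 15, no ICU stay), whatever is later observed.

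Severity is minor. The number affected is unknown and probably small. A reader might infer that this could decide MA1. On the assumed 50–90% failure-free range, 5 to 9 net patients in one arm would be needed to create the 10% difference from nothing. Under the second activity scenario in 16.4.2, that difference counts only alongside at least a 10% relative effect on the primary endpoint. The third scenario needs only 5%, with moderate effects on at least three secondary endpoints and one virologic endpoint. The affected endpoints are in the list for that section, though it is unclear whether key secondary endpoints count there. All scenarios also require a consistent overall pattern. The point is worth correcting because the imputation is avoidable, probably linked to outcome, and cheap to remove.

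**What to change.** 1. In 17.2, limit the trigger to prohibited medication taken during the treatment period (up to Day 14). Keep later users in follow-up, and state in the SAP that their observed outcomes to Day 28 are analysed.
2. State one CQ/HCQ rule for Days 15–28 in 9.3, 11.2.1, 11.2.2, 8.1 and the synopsis. The choice is clinical and belongs to the sponsor: either end the ban at Day 14, or continue it to end of study and write the exception into the permissive sentences. Under a continued ban, later use is recorded as a protocol deviation only.

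Optional tidying: 11.2.1 says "Arbidol and Colchicine are prohibited for centers in all countries" with no end date, whereas the 11.2.2 list stops at Day 14. Adding that limit to 11.2.1 and the synopsis would align them.

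The cost is wording in the next amendment and one line in the SAP. No new data are needed, since medications are already recorded until end of study and Day 28 assessments are already requested after discontinuation. The small downside is that a ban continued to end of study would be enforced only through deviation recording.
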